#### 2.1.4.3 Influenza COVID-19 Combination Vaccine

ICC vaccines, adjuvanted with Matrix-M1, have been studied in ferrets and hamsters. Groups of ferrets received two IM doses, separated by 21 days, of 15 or 60 µg of each of 4 HAs with Matrix-M1 adjuvant, and with or without 5 µg of SARS-CoV-2 rS. HAI antibody responses to all 4 HAs showed minimal dose response and no negative effect of co-administration with SARS-CoV-2 rS. hACE2 binding inhibition antibody responses to the SARS-CoV-2 S were slightly lower, but not significantly different, in the combined vaccine group relative to the monovalent of SARS-CoV-2 rS recipients. In a second experiment, hamsters were immunized

with two-dose regimens of 1 or 5  $\mu$ g of SARS-CoV-2 rS alone, or with qNIV comprising 2.5 or 10  $\mu$ g of each HA, or qNIV alone. All groups received a constant dose of 15  $\mu$ g of Matrix-M1 adjuvant with each injection. For each influenza strain examined, HAI titers and virus neutralization titers at two weeks after the first and second doses showed no clear dose-response and were comparable with or without of SARS-CoV-2 rS co-administration ([Massare 2021](#)). Similarly, anti-rS IgG levels induced by of SARS-CoV-2 rS showed no significant impact of influenza vaccine co-administration. hACE2 binding inhibiting antibodies were slightly, albeit not significantly, lower in animals receiving the combined vaccines ([Massare 2021](#)). At 21 days after the second dose, all hamsters were challenged intranasally with SARS-CoV-2. All animals immunized with either dose of SARS-CoV-2 rS, with or without qNIV, demonstrated accelerated clearance of SARS-CoV-2 subgenomic RNA from the upper airway, and essentially complete protection against weight loss, viral replication in the lower respiratory tract, and lung histopathology. Thus, co-administration with qNIV had no detectable effect on the potent protective efficacy of the of SARS-CoV-2 rS vaccine.

Additional supportive nonclinical study summaries can be found in the ICC IB ([Novavax 2021](#)).

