Factor (unit)	Role	Lower value	Upper value
SARS-CoV-2 rS (μg)	Continuous	2.5	22.5
HA per strain (μg)	Continuous	5	60

Table 6 shows the planned list of runs identified by the DOE platform within SAS JMP and number of planned replicates per run. The actual number of replicates providing data will be dependent on the enrollment into the study and exclusion of subjects from the PP Analysis Set. Runs 1 and 3, as well as 8 and 14, are identically specified.

Table 6 Planned List of Runs

Run	Replicates	Value for SARS-CoV-2 Factor	Value for HA Factor
1	40	22.5	60
2	40	2.5	10
3	40	22.5	60
4	40	7.5	10
5	40	22.5	10
6	40	7.5	35
7	40	22.5	5
8	40	2.5	60
9	40	7.5	5
10	40	2.5	5
11	40	22.5	35
12	40	2.5	35
13	40	7.5	60
14	40	2.5	60

Factor levels are treated as continuous coded values ranging from -1 to 1 so that each factor contributes equally to predicting the optimal response. The initial full regression model to be run is expressed as:

$$Y = \beta_0 + \beta_1 X_1 + \beta_2 X_2 + \beta_3 X_1 X_2 + \beta_4 X_1^2 + \beta_5 X_2^2 + \varepsilon$$

where:

Y is the response

X1 = coded antigen level for each HA flu strain

X2 = coded antigen level for SARS-CoV-2 rS

X1*X2 = interaction term for HA antigen level and SARS-CoV-2 rS antigen level

ϵ = error term with expected value of 0

SAS JMP will be used to fit a least-squares model for each response indicated in Table XX. Each run's replicate values may or may not be averaged across the subjects in the PP Analysis Set to determine the independent Y value for the run. An examination of the data will guide the decision and it will be documented in the report. Baseline measurement for each replicate may be included as covariate if no averaging is performed for a run's replicates. The initial full model will be run and significance of each term examined. A p-value <0.05 indicates that a term is significant. Non-significant terms will be removed and the resulting reduced model (for each response) will be fitted for exploration with a Predication Profiler tool. Desirability functions (ranging from 0 for lowest level to 1 for highest level) will be used to identify factor settings that optimize the set of responses. Weighting for each response may be considered. Factor setting(s) that lead to the highest overall desirability will be the level of HA and rS that optimize responses in Table XX.

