As a parallel analysis, SAS PROC RSREG will be used to run a response surface model that uses the dataset without first averaging the results of each run across replicates nor incorporating the baseline measurement into a fold-rise (i.e. use the data as-is). In this model, Y would be set as the antibody response value at the time point of interest, with BL being the corresponding measurement at Day 0. X1 and X2 have the same definition as the when the model is fitted within SAS JMP.

Example SAS code:

```
PROC RSREG DATA=X;  
MODEL Y=BL X1 X2 / LACKFIT COVAR=1;  
RUN;
```

The fit of the model is to be assessed by examining the p-value from the lack-of-fit test and plots of residuals for each factor. Significance of main, quadratic and interaction effects will also be assessed and reported.

The canonical analysis results from PROC RSREG provide information on the shape of the response surface. A maximum point is identified on the response surface by all eigenvalues being negative (a second order derivative test).

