11.3 Multiple Comparisons/Multiplicity

No multiplicity adjustment will be applied for the secondary immunogenicity endpoints.

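### SAP 7.4 reports the HA/rS setting with the highest fitted desirability without any measure of its sampling error, and its parallel RSREG analysis identifies a maximum by curvature alone

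*SAP*

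**What the plan says.** SAP 7.4 describes two analyses.

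**Desirability analysis in JMP.** Each response gets a full quadratic in HA and rS. The rule for keeping terms is "A p-value <0.05 indicates that a term is significant", followed by "Non-significant terms will be removed and the resulting reduced model (for each response) will be fitted for exploration with a Predication Profiler tool". The reported result is then defined: "Factor setting(s) that lead to the highest overall desirability will be the level of HA and rS that optimize responses in Table XX". (Table XX is an unresolved cross-reference, read here as Table 4, the list of ten responses.) On the factors, the SAP says: "Factor levels are treated as continuous coded values ranging from -1 to 1 so that each factor contributes equally to predicting the optimal response". Table 5 gives the limits as 5 to 60 µg HA per strain and 2.5 to 22.5 µg rS.

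**Parallel analysis in PROC RSREG.** The sample code has one modelling line, "MODEL Y=BL X1 X2 / LACKFIT COVAR=1", with no ridge or bounded search. The canonical analysis is read as follows: "A maximum point is identified on the response surface by all eigenvalues being negative (a second order derivative test".

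SAP 7.4 and Protocol 9.3.3 and 9.3.8 give no standard error, confidence region, resampling step or near-tie rule for the selected setting, and no interval for the predicted response there. SAP 7.4 has lack-of-fit and residual checks. Protocol 9.3.8 allows optional sensitivity analyses on selected data points. Nothing says what happens if the RSREG fit is a saddle, or if the two analyses disagree.

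**The concern.** Protocol 2.2 and SAP 1 make the identification of optimal HA and rS levels the main objective, so the located optimum is the study's chief product. The location of an estimated maximum is a noisy statistic when the surface is shallow: small errors in the coefficients can move it across the region while the predicted response hardly changes. A reader shown only the point cannot tell a well-located peak from an arbitrary place on a plateau. Protocol 2.2 also wants both antigen doses kept low, and for that aim the useful output is the range of settings that perform about as well as the best one.

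A shallow surface is plausible. In the ferret study in Protocol 2.1.4.3, "HAI antibody responses to all 4 HAs showed minimal dose response". That evidence is limited: it compared only 15 and 60 µg, and it does not address the rS dose.

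The RSREG rule raises a different problem. Negative eigenvalues show that the fitted quadratic bends downwards in every direction. They do not show that its top lies within the doses studied.

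**Working it through.** **1. What the plan's own precision figure implies.** SAP 1.2 states more than 99% power with 40 per group for a two-fold difference, and says that no power calculation was based on the DoE methods. Two-fold is log10(2) = 0.301. With power ≈ Φ(0.301 / (SD × √(2/40)) − 1.96):

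- SD 0.30: Φ(4.49 − 1.96) = 99.4%
- SD 0.35: 97.0%; SD 0.40: 92.0%
- SD 0.45: Φ(2.99 − 1.96) = 85%

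The documents give no SD, so the figure cannot be reproduced exactly. It implies an SD of at most 0.314 log10 for a two-group comparison, or 0.444 for a one-sample or paired reading. An SD range of 0.20 to 0.45 is therefore assumed below.

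**2. Precision of a comparison between two settings.** With the Table 6 design (14 runs × 40 = 560) and the SAP's full quadratic, SE = SD × √(v′(X′X)⁻¹v), where v is the difference between the two model rows. For 60/22.5 against 35/7.5 (HA/rS, µg) the square root is 0.161.

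| SD (log10) | SE | 1.96 × SE | 95% limits as a fold factor |
|---|---|---|---|
| 0.20 | 0.0322 | 0.063 | ×/÷ 1.16 |
| 0.30 | 0.0483 | 0.095 | ×/÷ 1.24 |
| 0.444 | 0.0715 | 0.140 | ×/÷ 1.38 |

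A true difference of 0.05 log10 (1.12-fold) is below the half-width even at SD 0.20.

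**3. Spread of the selected setting.** Trials were simulated on the Table 6 design with the five Day 70 responses of Table 4. The desirability was maximised inside the Table 5 limits. Ranges are 5th to 95th percentiles in µg. *Full* keeps all terms; *reduced* drops those with p ≥ 0.05.

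Monotone surfaces (assumed: effects in log dose, geometric-mean desirability). The three effects are the HAI rise over the HA range, the anti-S rise over the rS range, and the loss of anti-S due to HA.

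| Effects | SD | Model | HA | rS |
|---|---|---|---|---|
| 1.15-fold / 1.2-fold / 10% | 0.45 | both | 5-60 | 2.5-22.5 |
| same | 0.30 | both | most or all of the range | most or all of the range |
| 1.3-fold / 1.5-fold / 15% | 0.45 | full | 34-60 | 2.5-22.5 |
| same | 0.45 | reduced | 5-60 | 7.5-22.5 |
| same | 0.30 | full | about 39-60 | about 8.5-22.5 |
| same | 0.30 | reduced | about 44-60 | about 15-22.5 |

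At SD 0.20 even the weakest surface gives HA 38-60 under the full model.

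Interior peaks (600 trials per cell, 40 per group, reduced model), by fall-off from the peak:

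- 0.05 log10: whole region at every SD from 0.20 to 0.45.
- 0.10 log10: HA 34-45 and rS 13-20 at SD 0.20; whole region at SD 0.45.
- 0.20 log10: HA 35-41 and rS 13.5-16 at SD 0.30.

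On a flat surface the procedure still kept a term and named a setting in 60-69% of trials.

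**4. The eigenvalue rule.** The stationary point is s = −½B⁻¹b, where b holds the linear coefficients and B the quadratic ones. The eigenvalues depend on B alone. The location also depends on b and is not constrained.

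With HAI rising 1.5-fold in log HA dose, 46-60% of the fits with all eigenvalues negative had their stationary point outside the Table 5 ranges, and 52-58% of all fits were saddles (SD 0.20 to 0.45). At SD 0.45, 36% of fits had all eigenvalues negative, 56% were saddles and 8% minima. With 46% of the first group out of range, an in-range maximum arises in about 0.36 × 0.54 = 19% of trials. The saddles are expected: rS has no true effect on HAI in this surface, so the sign of its fitted curvature is close to a coin toss.

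A saddle can arise without noise. If HAI rises 0.10 log10 with log HA dose and falls 0.05 log10 with log rS dose, the fitted eigenvalues are −0.0241 and +0.0168. The rule then names no maximum, although a best setting within the region exists.

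**The case against.** - **The desirability search is in range.** A reader might infer that the reported optimum can fall outside the studied doses. The documents do not support this. The search works on factors with Table 5 limits coded −1 to 1 and would normally stay inside them, although the SAP does not say so. The out-of-range result belongs to the RSREG analysis alone.
- **RSREG describes shape.** The SAP presents its canonical analysis as information on the form of the surface, and no sentence makes its stationary point the chosen dose. The eigenvalue sentence is also correct as a second-derivative test. What stands is that the text identifies a maximum without asking where it is.
- **The plan does not commit to one dose.** It allows several settings, uses the result to inform selection, and foresees confirmation in a later Phase 2 study. The formulations are also compared directly with the reference vaccines, with 95% confidence intervals (SAP 7.2.1 and 7.2.2). This lowers the consequence. It does not supply the missing uncertainty, because a later study tests only what is carried forward.
- **The size depends on the SD.** The two-group reading of the power statement points to 0.31 or less, where the moderate surface is located much better than at 0.45. This stands. A reader might infer that most of the region is always indistinguishable from the optimum; that holds only for shallow surfaces or larger SDs.
- **Pruning gives some protection.** On a flat surface 31-40% of simulated trials kept no term. That guards against naming an optimum where there is none, but says nothing about how well a named one is located.

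**Conclusion.** The concern holds in two separate parts.

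First, the setting or settings with the highest fitted desirability are reported without sampling uncertainty. For shallow surfaces (1.15-fold, 1.2-fold, 10%) the location is close to undetermined at SD 0.30 to 0.45. For moderate effects (1.3-fold, 1.5-fold, 15%) it is usefully narrowed at SD 0.30, but at SD 0.45 it spans the whole rS range (full model) or the whole HA range (reduced model). A peak of 0.20 log10 or more is located well.

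Second, the RSREG rule establishes curvature only. In the surface examined, about half of the points it accepts lie outside the studied ranges, and over half of the fits give it no maximum. That the rule does not fix the location is mathematics and needs no assumption.

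The percentages rest on assumed SDs, correlations, surfaces and desirability scaling, and on Day 70 responses only, whereas Table 4 also lists Day 28. They show order of magnitude. Since the result is exploratory input to a later study, this should be corrected but does not invalidate the design.

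**What to change.** Amend SAP 7.4 before the biostatistics team is unblinded for the Day 70 analysis:

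(a) Bootstrap participants within formulation (for example 2,000 draws), repeating the whole sequence of fit, term selection and optimisation each time. Report the distribution of the selected setting and intervals for the predicted responses there. Also report intervals for the difference in predicted response between that setting, held fixed across draws, and other settings, and list as near-optimal those within a margin stated in advance. The setting must be held fixed because a difference from a re-maximised value can never exceed zero. The margin is needed because a non-significant difference is not equivalence. Present this as information for selection, not as a rule on which formulations may go forward.

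(b) For RSREG, report where the stationary point lies. Report also the maximum constrained to the Table 5 ranges, by a ridge or bounded search, and state whether it is interior or on the boundary.

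The cost is a modest resampling program and a revised paragraph, with no new data. The optimum will be presented as a region rather than a point.

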8 ADDITIONAL ANALYSES

8.1 Vital Signs

Vital sign measurements at all visits include temperature (oral or via forehead/ear reader), pulse rate, diastolic and systolic blood pressure (after participant is seated for at least 5 minutes), respiratory rate, and oxygen saturation. Temperature will be recorded and graded during general systemic reactogenicity evaluation. The other vital signs measurements will be recorded as

continuous variables. The measurement for baseline is the last set of vital signs taken immediately prior to first dose.

Descriptive statistics for vital signs will be presented by study vaccine group for all participants in the Safety Analysis Set including absolute means and SDs, minimum, maximum.

8.2 Physical Examinations

Physical examinations performed at post-baseline scheduled visits will be summarized by study vaccine group and by body system. For each body system examined, the number and percentage of participants with normal/abnormal results will be reported. The calculation of abnormal results will also be broken out by whether the abnormal result was considered clinically significant or not.

9 CONDUCT OF ANALYSES

As all analyses are descriptive, there are no interim analyses planned that require adjustment to Type I error.

After all participants have completed Day 70, and their data are cleaned, an analysis of the safety primary endpoints through Day 70 and relevant secondary/exploratory immunogenicity endpoints (HAI, MN₅₀, IgG) through Day 70 and possibly available CMI through Day 63. Immunogenicity Data through Day 70 will also be used in the response surface modeling covered under the exploratory analysis. At this point, members of the Novavax Biostatistics team will be unblinded as described in section 1.4.

After all participants have completed through Day 182 after first vaccination, and their data are cleaned, an analysis of all primary safety endpoints through Day 182 and relevant secondary endpoints/exploratory endpoints (HAI, MN₅₀, IgG and CMI) through Day 182 will be conducted.

10 COMPUTER METHODS

With the exception of DoE modelling, statistical analyses will be performed using SAS® version 9.4 or higher in a Windows environment. DoE modelling will primarily be performed using JMP Pro version 16 in a Windows environment, with PROC RSREG being implemented in SAS.

11 DATA HANDLING CONVENTIONS

All output will be incorporated into Microsoft Word or Excel files, or Adobe Acrobat PDF files, sorted and labeled according to the International Conference on Harmonisation (ICH) recommendations, and formatted to the appropriate page size(s).

Tabulations will be produced for appropriate demographic, baseline, and safety parameters. For categorical variables, summary tabulations of the number and percentage of participants within each category (with a category for missing data) of the parameter will be presented. For

continuous variables, the number of participants, mean and standard deviation (SD), median, minimum, and maximum values will be presented.

All references to analysis of GMT/GMFR/GMTR/GMEU/GMEUR will be interpreted as analysis of the \log_{10} of titer values or concentration values.

The individual HAI titer values, immunogenicity (MN_{50}) titer values and IgG concentration values recorded as below the LLOQ of the assay will be set to half LLOQ for the purposes of GMT/GMFR/GMTR/GMEU/GMEUR analyses. The LLOQ values will be provided by corresponding lab or CRO as part of the data transfer.

Medical history and AEs will be coded using MedDRA Version 24.1.

Each parameter will be reported with the below defined decimal numbers in [Table](#) .

Table 7 Decimal Numbers for Parameters

Parameter	Number of Decimal
Number of participants (e.g., N, N1, N2)	0
Percentage (%)	1
Mean	1 more decimal than raw data
Standard Deviation (SD)	1 more decimal than mean
Median, Min, Max	as same decimal as raw data
GMT, GMFR _{Post/Pre} , their corresponding 95% CIs	1
GMEU, GMFR _{Post/Pre} , their corresponding 95% CIs	1
GMTR, GMEUR, their corresponding 95% CIs	2
SPR (%), SCR (%), their corresponding 95% CIs	1

Note: For analysis of exploratory CMI response, up to 5 decimal numbers will be presented depending on number of significant digits for each parameter.

11.1 Baseline Definitions

For all analyses, baseline is defined as the last non-missing measurement prior to the first administration of the study material. For immunogenicity analysis, baseline will be the result from the sample drawn on the day of vaccination.

11.2 Adjustments for Covariates

Comparison of GMTR/GMEUR between the study vaccine groups will be adjusted for pre-vaccination titer.

11.3 Multiple Comparisons/Multiplicity

No multiplicity adjustment will be applied for the secondary immunogenicity endpoints.

11.4 Withdrawals, Dropouts, and Loss to Follow-up

Participants are free to withdraw from the study at any time upon written request. Participant participation in the study may be stopped at any time at the discretion of the investigator or at the request of the sponsor.

Participants may refuse further procedures (including study vaccination) but are encouraged to remain in the study for safety follow-up. In such cases where only safety is being conducted, participant contact could be managed via telemedicine contact (eg, telephone, web chat, video, FaceTime).

Vaccination with an approved or deployed SARS-CoV-2 vaccine alone will not require withdrawal from the study; and such participants will be encouraged to continue their participation.

Participants who withdraw, are withdrawn or terminated from this study, or are lost to follow up after signing the informed consent form (ICF) but prior to first study vaccination may be replaced. Participants who receive study vaccine and subsequently withdraw, are discontinued from further study vaccination, are terminated from the study, or are lost to follow-up will not be replaced.

Whenever possible, any participant who withdraws from the study prematurely will undergo all EOS assessments. Any participant who fails to return for final assessments will be contacted by the site in an attempt to have them comply with the protocol.

11.5 Missing, Unused, and Spurious Data

In general, there will be no substitutions made to accommodate missing data points. All data recorded on the eCRF will be included in data listings that will accompany the CSR. Partially recorded dates for on-study events should result in query to the site before undertaking the data handling steps below.

When tabulating AE and Concomitant Medications (exclusive of vaccinations prior to Dose 1) data, partial dates of event onset will be handled as follows:

- If the day of the month is missing, the onset date will be assumed to be the date of the Day 0 vaccination or first of the month, whichever is later, in order to conservatively report the event as treatment-emergent.
- If the onset day and month are both missing, the event onset will be coded to the date of the Day 0 vaccination or 1st January of the year, whichever is later, in order to conservatively report the event as treatment-emergent.
- A completely missing onset date will be coded as the date of the Day 0 vaccination, unless the end date suggests it could have started prior to this in which case impute the 1st January of the same year as the end date.
- No imputations will be made to event ending dates.

- When imputing a start date ensure that the new imputed date is prior to the end date of the AE or medication.

When tabulating Medical History or Previous Vaccination data, partial start dates of event will be handled as follows:

- For start date with a missing day and/or month, impute a missing day as the first of the month, and a missing month as January. The resulting date should be prior to the Day 0 vaccination and before the end date (full or partial date). A partial start date with an entirely missing ending date should result in a query to the site.
- For start date with a missing year, impute the year to be year of the ending date if it exists. Otherwise, the missing start date will be kept as missing.

For tabulations of AE, a top-level summary will be generated to report treatment-related AEs according to two conventions:

- No imputation of missing relationship to test article
- Consider the event to be treatment-related to test article.

Similarly, the top-level summary will report severe AEs according to two conventions:

- No imputation of missing severity
- Consider the event to be severe

Detailed presentation of AE data by SOC and preferred terms will be generated without first imputing missing relationship nor severity. As with missing dates, queries to the site should be undertaken before employing the reporting conventions described above.

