6.2 Concomitant Medication

Concomitant medications will include all medications (including any approved or deployed COVID-19 or influenza vaccine) taken by the participant from the time of signing the ICF

through 182 days after the first vaccination (or through the early termination visit if prior to that time). After Day 70, only those concomitant medications taken for any of the following events will be recorded: any MAAEs, SAEs, or AESIs (including PIMMCs).

The number (percentage) of participants who record one or more prior/concomitant medications (including vaccines) recorded on the Prior/Concomitant Medications eCRF will be summarized overall and by the study vaccine group and preferred drug name as coded using the WHO drug dictionary for all participants in the Safety Analysis Set. Multiple occurrences of medication usage for a participant will be counted only once within an ATC term and standardized medication name.

A separate listing of treatment-emergent new concomitant medications (including vaccines) will be presented.

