7.1.2 Unsolicited Adverse Events

Unsolicited adverse events are defined as any adverse events occurring within the 7-day window following vaccination and not specifically solicited in the diary, or any adverse event that occurs outside the 7-day diary solicitation period. All unsolicited AEs of any severity will be collected from the time of first study vaccination through Day 70 (ie, until 14 days after the second vaccination). Any relevant observations made prior to the first dose of study vaccine are to be recorded on the AE eCRF but will not be considered TEAEs and will be reported separately from TEAEs. The time periods for summary of adverse events are described at the end of this section. Summaries for other time periods may also be produced.

Unsolicited AEs will be coded by Preferred term (PT) and System Organ Class (SOC) using the latest version of Medical Dictionary of Regulatory Activities (MedDRA). Unsolicited AEs will be summarized overall and by study vaccine group then by SOC/PT as well as by severity (Mild, Moderate, Severe, or Potentially Life Threatening), and relatedness (not related,

related, not applicable) to the study vaccine. For multiple occurrences of an AE in the same participant, a participant will be counted only once, using the most severe or most related occurrence for the summarization by severity or relationship to the study vaccine, respectively. The number and percentage with its corresponding exact 95% CIs of unsolicited AEs will be calculated using Clopper-Pearson method.

An MAAE is defined as an AE that leads to an unscheduled visit to a healthcare practitioner. AESIs include PIMMCs, AEs specific to complications of COVID-19 (listed in [Error!](#)

[Reference source not found.](#)), or other potential AEs that may be determined at any time by regulatory authorities as additional information concerning COVID-19 is obtained. All MAAEs and AESIs (including PIMMCs and complications to COVID-19) will be collected from the first study vaccination through Day 182 after first vaccination. An AESI must be reported as if it is an SAE. SAE is defined as an event considered “serious” if, in the view of either the Investigator or Sponsor, it results in any of the outcomes listed in Section 8.1 Protocol. All SAEs will be collected from signing of informed consent until completion of the EoS.

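### The SAP's partial-date rule assigns Day 0 to records whose known month or year lies before Day 0, so ongoing prior medications are listed as treatment-emergent.

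*SAP*

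**What the plan says.** SAP section 11.5 covers partial start dates of AEs and concomitant medications together and exempts only vaccinations before the first dose: "When tabulating AE and Concomitant Medications (exclusive of vaccinations prior to Dose 1) data, partial dates of event onset will be handled as follows".

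- Day missing: "the onset date will be assumed to be the date of the Day 0 vaccination or first of the month, whichever is later".
- Day and month missing: "the event onset will be coded to the date of the Day 0 vaccination or 1st January of the year, whichever is later".
- The purpose given for both is "in order to conservatively report the event as treatment-emergent".
- Date completely missing: Day 0, "unless the end date suggests it could have started prior to this", in which case 1 January of the end-date year is used.
- General check: "When imputing a start date ensure that the new imputed date is prior to the end date of the AE or medication".

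The section also asks for a site query before imputation, worded for on-study events. Medical History and previous vaccinations have a separate rule that keeps the imputed start before Day 0.

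Two other parts of the SAP depend on these dates. Section 6.2 states: "A separate listing of treatment-emergent new concomitant medications (including vaccines) will be presented". Section 7.1.2 says that relevant observations "made prior to the first dose of study vaccine are to be recorded on the AE eCRF but will not be considered TEAEs". Protocol section 8.2.3.1 defines a treatment-emergent AE (TEAE) as one that occurs or worsens on or after the first dose.

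**The concern.** Imputing towards Day 0 is sound when the recorded part of the date leaves open whether the start came before or after vaccination. The SAP does not limit the rule to that case. It also covers records whose month or year already shows a start before Day 0, and it overwrites that information.

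For AEs this conflicts with the TEAE definition and with the SAP's own statement on pre-dose observations. For medications, a long-standing drug with an approximate start date appears as newly started after vaccination. That can send safety reviewers after a false lead. If programmers notice the problem only when the tables are run, they would have to settle it ad hoc.

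**Working it through.** The plan gives no figure to reproduce on this point, so the check applies the rule as written to test dates.

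**Formula.** Let D0 be the date of the Day 0 vaccination. Let F be the first of the recorded month, or 1 January of the recorded year if the month is missing. The SAP start date is S = max(D0, F), and a record is treatment-emergent if S ≥ D0. Since max(D0, F) can never be below D0, the formula cannot class any partial-date record as prior. Only the end-date check can intervene.

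**Assumption.** D0 = 20 Sep 2021. This is illustrative; the protocol synopsis estimates a September 2021 start. The proposed rule is the one set out under the fix.

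| Recorded start | End | SAP rule | Proposed rule |
|---|---|---|---|
| Mar 2015 | ongoing | max(20 Sep 2021, 1 Mar 2015) = 20 Sep 2021, emergent | 1 Mar 2015, prior |
| 2015 | ongoing | max(20 Sep 2021, 1 Jan 2015) = 20 Sep 2021, emergent | 1 Jan 2015, prior |
| Aug 2021 | ongoing | 20 Sep 2021, emergent | 1 Aug 2021, prior |
| Aug 2021 | 10 Oct 2021 | 20 Sep 2021, emergent; passes end-date check | 1 Aug 2021, prior |
| Aug 2021 | 5 Sep 2021 | 20 Sep 2021, after the end date; check fails, no replacement given | 1 Aug 2021, prior |
| Sep 2021 | ongoing | 20 Sep 2021, emergent | same |
| 2021 | ongoing | 20 Sep 2021, emergent | same |
| Oct 2021 | ongoing | 1 Oct 2021, emergent | same |
| completely missing | 5 Sep 2021 | 1 Jan 2021, prior | not changed |

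**Reading the table.**

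1. Rows 1 to 4 are coded treatment-emergent although the recorded part proves a start before vaccination. The end-date check does not help, because the record is ongoing or ended after Day 0.
2. Row 5 is undefined. The check rules out Day 0, but the fallback in section 11.5 is written only for a completely missing date.
3. Rows 5 and 9 have the same end date. The record with no start information is correctly classed as prior, while the one with a known earlier month has no valid result.
4. Rows 6 to 8 are ambiguous or later dates. Both rules agree on them, so the intended conservatism is kept.

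**The case against.** The case for leaving this alone is mostly about impact, and much of it stands.

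- **AE exposure is small.** Protocol section 8.2.2 sends occurrences that begin before the first dose to Medical History, which has its own date rule. Unsolicited AEs are collected from first vaccination, and protocol section 6.1.1 combines screening with Day 0. The AE records at risk are mainly pre-dose observations entered on the AE form and serious AEs between consent and dosing. Each would also need a missing day and a month before that of Day 0. The SAP says pre-dose observations are reported separately in any case.
- **The medication summary does not move.** SAP section 6.2 and protocol section 9.3.6.3 tabulate prior and concomitant medications together, so an altered start date changes no count there. The affected output is a listing. The data listings should also contain the recorded partial date.
- **Queries come first.** That instruction covers on-study AEs. It is less clear that it covers a drug started years earlier, and a query may not recover a day the participant has forgotten.
- **The rule is deliberately conservative and applies to every group.** No between-group bias is shown, and the safety analysis is descriptive. But conservatism is a reason to resolve doubt towards Day 0, and these dates leave no doubt.

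A reader might infer that every record with an earlier month or year is misclassified. The documents do not support that, because the end-date check bars Day 0 for records that ended before it. A reader might also infer that primary TEAE rates are materially inflated. The collection rules above make that unlikely.

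**Conclusion.** The rule is wrong as written for one defined class: AE or medication records with a partial start date whose known month or year is wholly before Day 0, and which are ongoing or ended after Day 0. These are coded treatment-emergent against their own recorded information. A second class, records that ended before Day 0, has no defined start date.

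The practical effect falls mainly on the listing of new treatment-emergent medications. Approximate start dates are foreseeable there: participants are 50 to 70 years old, protocol section 5.4 allows stable, managed conditions such as mild hypertension, and current drugs are reviewed at screening.

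The documents give no frequency of partial dates, so the number of records or participants cannot be calculated. A reader might try a guess such as 10% to 30% of 640 participants (64 to 192), but nothing in either document supports those percentages. The mechanism follows from the text and does not depend on the date assumed for Day 0. No endpoint definition, group comparison or dose-selection model is shown to be affected. The correction is still worth making because it is specific and nearly free.

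**What to change.** In SAP section 11.5, replace the two partial-date bullets for AEs and medications with three cases:

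1. If the known month (or the known year, when the month is missing) is the same as that of Day 0, and the end date does not rule it out, impute Day 0.
2. If the known month or year is earlier than that of Day 0, or the end date precedes Day 0, impute the first of the recorded month or 1 January of the recorded year, and class the record as prior.
3. If the known month or year is later, keep the current rule.

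Case 2 also supplies the fallback date that the end-date check lacks. The cost is two or three sentences in the SAP and a small change to the date-imputation program, with no new data. Make the change before the tables and listings are run.
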